5.2 Pharmacokinetic Assessments

Not applicable.

6 ENDPOINTS AND VARIABLES

6.1 **Primary Variables**

The endpoints to assess efficacy (exploratory) will be adapted to the patient's age and the corresponding tests they are able to perform. When feasible the following will apply in accordance with standard clinical practice:

- Muscle strength measured using the modified Medical Research Council (MRC) scale to evaluate neck flexors, shoulder abductors, elbow flexors and extensors, wrist extensors, finger flexors, hip flexors, knee flexors and extensors, posterior foot flexors and plantar flexors.
- Clinical Global Impression (CGI) Scores given to caregivers and assessed by the investigators
- Number and frequency of adverse events (AEs), serious adverse events (SAEs) and AE leading to treatment discontinuation, throughout the study while on treatment with mexiletine
- Incidence of adverse events of special interest (AESI)
- Description over time of efficacy outcomes obtained from clinically indicated tests as per the treating physician typical clinical practice and according to patient's age and cohort.
- Any changes in frequency, treatment interruptions of mexiletine.

6.2 Secondary Variables

- Description over time of outcomes of mexiletine use including dosing, formulation used, method of administration, acceptability and palatability as per the data collected by the treating physician according to age and cohort.
- The treating physician with elaborate a brief text with risk-benefit conclusions using the information from both the primary and secondary variables.

ASSESSMENT OF EFFICACY

Data Interpretation of Instruments/Scales

The efficacy endpoints chosen for the study are based on those that have been commonly used during routine clinical practice in adults (Logigian *et al.*, 2010; Statland *et al.*, 2012a; Statland *et al.*, 2012b), but they have been adapted according to the patient's age and ability to participate in the efficacy evaluation. Moreover, the approach to and the scope of efficacy endpoints has been accepted by the Regulatory Authorities (in particular the Paediatric Committee; PDCO) during the evaluation and discussion on the paediatric investigation plan (PIP) that this protocol is specifically designed to support. However, in this observational study the performance of these tests is not mandated by protocol or pre-scheduled. They will only be performed during the study according to routine clinical practice for the treatment of patients with myotonias at the discretion of the treating clinician.

I. Faces scale

A Faces (or other symbol) self-reported scale for children aged 6 years will be used to score muscle stiffness (myotonia severity) as by the patient. This type of scale has been validated and is considered suitable for use in at least a subset of the age group proposed (Tsze *et al.*, 2013). Muscle stiffness is commonly used as either a primary or secondary measure of efficacy in myotonic disorders clinical trials.

Similarly, the Faces scale will be used to assess pain, weakness and tiredness in study participants as secondary endpoints. As above, the Faces for severity score of pain, weakness and tiredness as self-reported will be constructed the same as for the stiffness score with a 10 cm straight horizontal line having the endpoints "no [symptom] at all" and "[symptom] as worst possible

II. Hand Grip Myotonia Test

The score of handgrip myotonia as quantitatively measured using a commercially available grip dynamometer and computerised capture system. In standardised conditions (i.e. in a room at controlled temperature, after a definite period of rest), maximum voluntary contractions following forced right hand grip will be recorded and the time to relax from 90% to 5% of maximal force will be determined using automated analysis software (Moxley *et al.*, 2007; Logigian *et al.*, 2010; Statland *et al.*, 2012b).

III. Action myotonia in eyelid muscles and right hand flexor muscles (Grip myotonia)

Subjects will be asked to squeeze their eyes closed for 5 seconds then rapidly open them; and make a tight fist for 5 seconds then rapidly open. Five trials of each manoeuvre will be performed in sequence at each visit and the time measured on a stopwatch (Statland *et al.*, 2012b).

IV. Timed-up and Go (TUG) Test

The Timed "Up and Go" Test (Podsiadlo and Richardson, 1991; Trip *et al.*, 2009a) measures, in seconds, the time taken by an individual to stand up from a standard arm chair (approximate seat height of 46 cm, arm height 65 cm), walk a distance of 3 meters (approximately 10 feet), turn, walk back to the chair, and sit down. This clinical test, developed in a medical setting, asks subjects to wear their regular footwear and use their customary walking aid (none, cane, walker). No physical assistance is given. They start with their back against the chair, their arms resting on the armrests, and their walking aid at hand. They are instructed that, on the word "go" they are to get up and walk at a comfortable and safe pace to a line on the floor 3 meters away, turn, return to the chair and sit down again. The subject walks through the test once before being timed in order to become familiar with the test. Either a stopwatch or a wristwatch with a second hand can be used to time the trial. This test is only appropriate for children ≥ 3 years of age.

V. Medical Research Council (MRC) scale

The modified Medical Research Council (MRC) scale can be used to evaluate neck flexors, shoulder abductors, elbow flexors and extensors, wrist extensors, finger flexors, hip flexors, knee flexors and extensors, posterior foot flexors and plantar flexors (MRC, 1975; Verreydt *et al.*, 2022). The MRC scale of muscle strength uses a score of 0 to 5 to grade the power of a particular muscle group in relation to the movement of a single joint (score 0 corresponds to no contraction, 3 active movement against gravity and 5 equates to normal power).

VI. Paediatric Quality of Life Questionnaire (PedsQL)

Changes in health-related quality-of-life as measured by the PedsQLTM Quality of Life (version 4.0) and Neuromuscular modules (version 3.0). These multidimensional scales assess the frequency of health problems using generic and disease-specific approaches, respectively. Subjects and/or parent or proxies report a score of 0 to 4 (never to almost always) and questionnaires are tailored to age groups. The Quality of Life module consists of 23 questions that are further divided into physical, emotional, social and school functioning subsets. The 25-question PedsQLTM Neuromuscular module was created as a more specific tool to measure health-related quality of life for musculoskeletal diseases such as Duchenne's muscular dystrophy and Spinal Muscular Atrophy (Iannaccone *et al.*, 2009; Davis *et al.*, 2010). It is subdivided into symptom/function, communication and family resource dimensions. Greater scores indicate morbidity and illness burden compared to healthy controls, the latter scoring no less than 80 in all scales (Varni *et al.*, 2002).

VII. Clinical Global Impression (CGI) scores

This will be evaluated by a caregiver and by the investigator. Efficacy will be evaluated on a 4-point scale as very efficient, good, fair or poor.

VIII Acceptability of mexiletine administration

Acceptability of different modes of mexiletine administration (i.e., capsule, sprinkled on food and/or gastric (enteral) tube where such formulations are used), and the factors that govern the route of administrations in paediatric patients will be assessed by reviewing the patient records, interviewing patients and their caregivers. Any difficulty in swallowing or compliance will be noted and if capsules were opened and content was taken, details should be recorded accordingly.

IX Palatability

Palatability of alternative administration (capsule content with milk/juice or sprinkled on food)will be recorded . Any complaint of bad taste or numbness will be inquired and recorded in the EDC or CRF accordingly.

X. FLACC (face, legs, activity, crying, and consolability) scale.

Pain is assessed by the investigator using the FLACC (face, legs, activity, crying, and consolability) scale (Drendel *et al.*, 2011), as a secondary endpoint, for Cohort 1 (\geq 6 months and <6 years). Each behaviour is scored from 0 to 2, with the highest possible cumulative score being 10 (most pain).

XI. PIPP (Premature Infant Pain Profile) scale.

Pain is assessed by the investigator using the PIPP (Premature Infant Pain Profile) scale (Stevens *et al.*, 2010), as a secondary endpoint for infants and toddlers < 6 months.

Protocol No. MEX-NM-401 Version No.: 1.0 Dated: May 30th 2024

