Congenital DM1 shows a distinct clinical phenotype with distinct clinical features. These patients present at birth with marked generalised hypotonia and hyporeflexia and difficulties breathing and feeding which cause respiratory distress that needs assisted ventilation. Mortality in congenital DM1 during the neonatal period has been estimated at between 30% and 40% of patients. Some children who survive may die later from sudden infant death syndrome, or from respiratory failure (Hageman *et al.*, 1993). In severely affected patients surviving the neonatal period, as in less severely affected patients, the disease course is very much the same: the most constant feature is mental delay, preceded by speech and language delay, that exists in all cases and progressively worsens after several years of evolution. In these forms, signs of central nervous system dysfunction predominate, with mental deficiency and/or psychiatric disturbances. Motor development is delayed in most cases, the children becoming ambulant after the age of 2 years. But in terms of muscular weakness and the development of myotonic syndrome, disease progression is markedly variable from one patient to another (Echenne and Bassez, 2013).

DM2 is not normally diagnosed until adulthood with symptoms beginning in the second to sixth decade (median age 48 years) with variable manifestations including early-onset cataracts (younger than 50 years), varying grip myotonia, thigh muscle stiffness, and muscle pain, as well as weakness (Meola and Cardani, 2015b). Overall, it is considered that myotonia is less apparent in DM2 compared with DM1, being difficult to elicit by standard electromyography (EMG) testing except for proximal muscles such as the tensor fascia lata and vastus laterali. In cases of late-onset DM2, myotonia may only appear by EMG testing after examination of several muscles. In general, patients with myotonic dystrophy type 2 have clinical symptoms that are usually milder (Turner and Hilton-Jones, 2010).

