3.3 Selection of Study Population

3.3.1 Inclusion Criteria

- 1. Male or female patients from birth to less than 6 years
- 2. A genetically confirmed diagnosis of NDM or DM (DM1or DM2), as per the treating clinician.
- 3. Presence of clinical symptoms of myotonia (hand grip myotonia, myotonia in the leg muscles, any other myotonia symptoms) to be confirmed by the treating clinician.
- 4. Patients already receiving mexiletine treatment or who are clinically considered for mexiletine treatment as per the treating physician judgement.
- 5. No history of or significant cardiac abnormalities as determined by a cardiologist's assessment of the ECG and echocardiogram performed prior to enrolment in the study or as per the treating physician standard of care (NaMuscla SmPC, 2023)
- 6. No known history or signs and symptoms of any significant liver disorder as per treating physician.
- 7. No known clinically relevant abnormal laboratory investigations for haematology, biochemistry, and urinalysis values at screening (or based on values obtained within 3 months prior to screening in patient's medical record) that could affect the study objectives as judged by the treating physician.
- 8. Parent or legal guardian able to provide assent to study participation and to sign the written informed consent prior to study entry and perform any study-related activity.

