8.13 Efficacy Analysis

When possible and according to age, the actual Faces scores and the change from baseline in Faces score for muscle stiffness, pain weakness and fatigue will be summarised over time.

Change from baseline in time (in seconds) to relaxation of hand muscles and reduction in relaxation time from the first to the third/fifth contraction and time (in seconds) for Timed-up and go (TUG) test will be summarised over time from screening to week 104.

Quality of life data will be presented descriptively by visit along with the change from baseline.

The observed values of Clinical Global Impression Scores and the change from baseline in Clinical Global Impression Score from baseline to Week 104 will be summarised.

The observed values of Myotonia Behaviour Scale Scores and the change from baseline in Myotonia Behaviour Scale Score from baseline to Week 104 will be summarised.

When performed, changes in clinical laboratory values from Screening to Week 104 will be summarised.

A separate Statistical Analysis Plan will be prepared.

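### The 4-point CGI has no level for worsening and does not define 'poor', so on this scale a child who deteriorates cannot be told apart from one who does not respond

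*Protocol*

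**What the plan says.** The Assessment of Efficacy part of the protocol (item VII, after Section 6.2) defines the CGI. On the raters it says "This will be evaluated by a caregiver and by the investigator", and on the response options "Efficacy will be evaluated on a 4-point scale as very efficient, good, fair or poor". It gives no anchor for any of the four labels, and no other section gives a fuller scale.

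Section 6.1 lists among the primary variables "Clinical Global Impression (CGI) Scores given to caregivers and assessed by the investigators". The only other efficacy instrument named in that list is muscle strength on the modified MRC scale. The same section marks efficacy as exploratory and dependent on age: "The endpoints to assess efficacy (exploratory) will be adapted to the patient's age and the corresponding tests they are able to perform".

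For the analysis, Section 8.13 plans descriptive summaries; its sentence on this scale begins "The observed values of Clinical Global Impression Scores and the change from baseline in Clinical Global Impression Score from baseline to Week 104 will be", and the Synopsis plans the same for both raters. Inclusion criterion 4 (Section 3.3.1) admits "Patients already receiving mexiletine treatment or who are clinically considered for mexiletine treatment as per the treating physician judgement". Section 6.2 has the treating physician write a short risk-benefit conclusion from the primary and secondary variables together.

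**The concern.** The response set runs from strong efficacy down to *poor* and stops there. A child who is no better and a child who is worse than before treatment can both only be rated *poor*. The missing *worse* level is the stronger half of the point. A rater can reasonably use *poor* for little or no effect, but nothing in the wording lets a rater record deterioration as such.

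This matters because the study is open-label and single-arm, and the rating is given by the caregiver and the investigator. It also goes into the physician's risk-benefit text. A global rating that can express degrees of benefit but no deterioration enters that text from one side only.

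The analysis section has a related difficulty. The CGI rates how well the drug works, yet a change from baseline is planned for all children. A child who is only being considered for mexiletine at entry has no drug efficacy to rate at baseline.

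**Working it through.** **Inputs from the protocol**
- CGI levels: 4. Levels that denote worsening: 0. Levels explicitly labelled no effect: 0. Anchors for *poor*: none (Assessment of Efficacy, item VII).
- Sample size: at least 4 children in cohort 2 and at least 6 in cohort 1, so 4 + 6 = 10. This reproduces the stated minimum of 10 (Section 8.8). The figure was agreed with the PDCO, was not derived from a hypothesis, and is not challenged here.
- No alpha, power or effect size is stated, and none is needed for this point.

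**Step 1: what the table can distinguish.** The split below is assumed for illustration. Take N = 10, with 5 children rated *good* and 5 who do not benefit, of whom w got worse and 5 − w are unchanged. Net improvement is improved minus worse, that is 5 − w.

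| w | 4-point CGI: good / poor | Improved / unchanged / worse | Net |
|---|---|---|---|
| 0 | 5 / 5 | 5 / 5 / 0 | +5 |
| 1 | 5 / 5 | 5 / 4 / 1 | +4 |
| 2 | 5 / 5 | 5 / 3 / 2 | +3 |
| 3 | 5 / 5 | 5 / 2 / 3 | +2 |
| 4 | 5 / 5 | 5 / 1 / 4 | +1 |
| 5 | 5 / 5 | 5 / 0 / 5 | 0 |

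Six different outcomes give one CGI table. With 10 children, each one is 1/10 = 10% of that table.

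**Step 2: how likely it is that the missing level would be needed.** The protocol gives no rate of worsening, so a range is assumed. The chance of at least one worsened child among 10 is 1 − (1 − p)^10:
- p = 5%: 1 − 0.95^10 = 40%
- p = 10%: 1 − 0.90^10 = 65%
- p = 20%: 1 − 0.80^10 = 89%
- p = 30%: 1 − 0.70^10 = 97%

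These figures do not separate drug effect from disease course. They show only that the level would probably be used unless worsening is rare.

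**Step 3: whether change from baseline supplies the missing information.**
- *Child already on mexiletine at entry.* A move from *good* to *poor* is visible. It shows loss of rated efficacy, not that the child is worse than before treatment.
- *Child not yet on mexiletine at entry.* There is no efficacy to rate at baseline, so the planned change is undefined.

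The planned analysis therefore does not recover the lost distinction for either group.

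**The case against.** The strongest reply is that the CGI item rates efficacy and harm is recorded elsewhere. That is largely right.
- Section 6.1 also lists adverse events, serious adverse events, events leading to discontinuation and events of special interest as primary variables. Section 8.1.3 requires disease signs to be reported as adverse events when the investigator judges them a worsening.
- The MRC scale can fall as well as rise: "The MRC scale of muscle strength uses a score of 0 to 5 to grade the power of a particular muscle group". PedsQL, the pain scales and the timed tests can also deteriorate where they are performed.

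A reader might therefore be tempted to say that net harm cannot appear in this study, or that the CGI cannot inform the risk-benefit conclusion. The documents support neither statement. The gap is on this scale only. Adverse-event reporting does not close it fully, because it gives event counts, not a distribution of improved, unchanged and worse, and no caregiver rating of worsening.

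Two other stronger readings also fail.
- A reader might count three favourable labels out of four and infer that 75% of ratings will look positive. That assumes labels are chosen at random and that *fair* means benefit; the protocol says neither.
- A reader might take the sentence in Section 1.1.1 that "disease progression is markedly variable from one patient to another" as a forecast that myotonia will worsen in this population. It concerns congenital DM1, and the steady worsening described there is of mental delay.

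The protocol also reports PDCO acceptance of the approach to and scope of the efficacy endpoints. It does not say that the response labels were reviewed. Nor can this be left to the statistical analysis plan, because response options are fixed when the data are captured.

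**Conclusion.** The point stands as a cheap improvement, not as a must-fix. On the CGI, non-response and deterioration cannot be separated, now or in later analysis. In the assumed example this hides a range of net improvement from +5 to 0 among 10 children. Its weight is moderate: the CGI is one of only two efficacy scales named among the primary variables and feeds the risk-benefit text, but efficacy is exploratory and descriptive and other measures can record worsening. The baseline problem follows directly from inclusion criterion 4 and affects only children not yet treated at entry.

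The conclusion assumes that the eCRF uses the four labels as the protocol words them, without further anchors.

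**What to change.** In item VII of Assessment of Efficacy and in the eCRF, for both caregiver and investigator:
1. Keep the four labels and add two separate levels, *no effect* and *worse*. Define *worse* as worse than before mexiletine, so that *poor* is left for a small, unsatisfactory effect.
2. Tabulate the full distribution by rater. For comparison with any study that used the 4-point item, collapse *no effect* and *worse* into *poor*.

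In Section 8.13 and the matching Synopsis text, for children not yet on mexiletine at entry, replace the change from baseline in CGI by the on-treatment rating at each visit.

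The cost is one eCRF item and a few sentences. For children already treated at entry, a rating against the pre-treatment state depends on recall or records; the retrospective efficacy data that Section 3.2 already plans to collect, where available, may help. Replacing the item with a full symmetric scale of change is more debatable: it leans more heavily on that recall and has no baseline value, so the planned change from baseline would have to go for every child.

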7 ASSESSMENT OF PHARMACOKINETICS

Not applicable.

8 ASSESSMENT OF SAFETY

The assessment of safety will be performed according to the collection of AEs during routine clinical practice visits by the treating physician, and medical monitor.

8.1 Adverse Events

Definitions

The definitions for AEs and SAEs are given below. It is of the utmost importance that staff involved in the study is familiar with the content of this section. The Principal Investigator is responsible for ensuring this.

8.1.1 Adverse Event

An AE is defined as any untoward medical occurrence in a patient or clinical investigation patient administered a pharmaceutical product and which does not necessarily have a causal relationship with this treatment. An AE can, therefore, be any unfavourable and unintended sign, symptom or disease (including intercurrent illness), deterioration of a pre-existing illness, accident, any suspected drug reaction, or a clinically relevant change of laboratory values temporally associated with the use of a medicinal (investigation) product, whether or not related to the medicinal (investigational) product and/ or study treatment.

A treatment emergent AE (TEAE) will be defined as an AE that begins or that worsens in severity after at least one dose of study drug has been administered.

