Data will be entered at baseline upon patient enrolment and entered periodically thereafter for all routine clinical practice patient visits. For example, all laboratory values collected at routine clinical visits occurring between month 6 and month 12 of a patient's participation in the registry should be entered at the 12-month time point. All data will include the date each assessment was performed. Where available, additional retrospective data will be collected. Retrospective data will be focussed primarily on patterns of mexiletine use and dose adjustments as well as any efficacy assessments. Retrospective safety data will also be recorded, especially in relation to any AEs that affect dosing, SAEs or AESIs, but there will be no requirement to report any retrospective AEs prior to signing the informed consent. In cases where retrospective data are captured, this will be recorded from first mexiletine prescription up to the baseline visit or to the maximum age of eligibility for entering into the trial (that is, up to 6 years). For eligible patients who provide informed consent, data elements will be extracted from the information routinely recorded in the medical records and transcribed in to the electronic Case Report Forms (eCRF). Safety, treatment administration and efficacy assessments will be collected during the visits. AEs will be collected from the time informed consent is given to end of treatment.

No drug safety monitoring committee (DSMB) will be created.

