8.12 Analysis Population

Safety Population: Safety population will comprise of the subjects who received at least one dose of mexiletine after the ICF was signed by their parents or legal guardians.

Intent to Treat (ITT) Population: ITT population will comprise of the subjects who have taken at least one dose of the study treatment and have at least one post-enrolment assessment done.

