8.14 Safety Analysis

All summaries of adverse events will use only treatment emergent adverse event (TEAE) records.

In general, events will be described by counts and percentages.

Following information will be summarized for TEAEs.

- Overall Summary of TEAEs
- TEAEs by preferred term and System Organ Class (SOC)
- Treatment Related TEAEs by preferred term and SOC
- TEAEs by preferred term and SOC, Maximum Severity and Relationship
- Serious TEAEs by preferred term and SOC

• TEAEs leading to discontinuation of study drug by preferred term and SOC

Also, listing of all adverse events will be provided. The listing will include Adverse event number, description, preferred term, SOC, Start and End Date, Seriousness, Frequency of Occurrence, Severity, Action taken regarding study treatment, outcome, relationship to study treatment.

When collected laboratory and vital signs parameters will be summarised descriptively. Laboratory tests done at screening will be considered baseline.

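### The TEAE definition behind every adverse event summary has no end tied to the last dose and does not itself confine events to the study period, so it does not match the on-treatment primary safety variable

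*Protocol*

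**What the plan says.** Section 8.1.1 of the protocol calls an adverse event treatment-emergent if it "begins or that worsens in severity after at least one dose of study drug has been administered". It names no consent date and no interval after the last dose. Section 8.14 then states: "All summaries of adverse events will use only treatment emergent adverse event (TEAE) records".

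Section 6.1, like the synopsis, sets a different window for the primary safety variable: events are counted "throughout the study while on treatment with mexiletine".

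Three other sets of rules bear on which events can reach the tables:

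- **Entry.** Section 3.3.1, criterion 4, admits "Patients already receiving mexiletine treatment or who are clinically considered for mexiletine treatment". The first dose can therefore precede consent.
- **Retrospective data.** Section 3.2 provides for past safety events to be captured too, with the emphasis on serious events, events of special interest and those that changed dosing. It makes this optional, however: "there will be no requirement to report any retrospective AEs prior to signing the informed consent". The same section sets the look-back period for any such data: "this will be recorded from first mexiletine prescription up to the baseline visit".
- **Collection and population.** Sections 3.2 and 8.1.3 run adverse event collection from consent to EOT, and section 8.1.4.2 has serious events reported from consent to the final visit. The Safety population in section 8.12 comprises "subjects who received at least one dose of mexiletine after the ICF was signed".

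**The concern.** Safety is part of the primary objective, and two fixed protocol rules give different answers on which events count. An analysis can follow sections 8.1.1 and 8.14, or it can follow section 6.1. It cannot follow both for an event that occurs after mexiletine has been stopped, or for one that preceded consent in a child already treated.

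At the end of the window, section 8.1.3 makes newly emergent or worsening disease signs, including progression, reportable as adverse events. In a child off drug, such an event could appear in a table headed treatment-emergent.

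At the start, retrospective capture favours events that changed dosing, serious events and events of special interest, with no duty to report the rest. Pooled with complete prospective capture, these events could raise the serious share and the share linked to dose changes. The analysis is descriptive and the minimum sample is 10, so a few records can shape the picture.

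**Working it through.** The protocol states no figure on this point. The sample size is an agreed minimum without a formula, so there is nothing to reproduce. The check compares windows and then sizes the gap.

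**1. Windows side by side**

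| Rule | Starts | Ends |
|---|---|---|
| TEAE definition (8.1.1), sole basis of summaries (8.14) | after the first dose, whenever given | not stated |
| Primary safety variable (6.1) | in study and on mexiletine | when mexiletine stops |
| Adverse event collection (3.2, 8.1.3) | consent | EOT |
| Retrospective safety data (3.2) | first prescription | baseline visit, or the maximum age for entry |
| Safety population (8.12) | restricts children, not event dates | – |

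The collection rule caps the TEAE window at EOT, not at the last dose. It closes the start only if retrospective events are kept out of the adverse event records, which the protocol does not say.

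**2. When EOT falls after an early stop**

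Section 3.2 gives two routes: the first routine visit after at least 2 years from entry, or 2 weeks after the last intake following 2 years of treatment. Neither describes a child who stops before 2 years. Section 4.1.1.2 asks only that EOT assessments be attempted after permanent discontinuation and gives no timing. Section 3.3.3 lists treatment discontinuation apart from study withdrawal, and section 1.4 requires every participant to be followed for at least 2 years. Continued follow-up off drug is therefore possible, but so is an EOT at the time of stopping.

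**3. Size at the end of the window (stop weeks are assumptions)**

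Inputs: 104 weeks of follow-up (synopsis) and at least 10 children (section 8.8), so 10 × 104 = 1,040 patient-weeks. For a stop at week s and EOT at week 104, off-drug weeks = 104 − s.

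| Stop week s | Off-drug weeks | Share of that child's follow-up | Share of 1,040 patient-weeks | Weeks removed if the TEAE window ends 2 weeks after last dose |
|---|---|---|---|---|
| 13 | 91 | 91/104 = 87.5% | 8.75% | 89 |
| 26 | 78 | 78/104 = 75% | 7.5% | 76 |
| 52 | 52 | 52/104 = 50% | 5.0% | 50 |

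The 2 weeks are borrowed from the EOT rule purely for illustration. If EOT takes place at discontinuation, off-drug time is close to 0 in every row.

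**4. Size at the start of the window**

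The look-back runs from first prescription and eligibility ends below 6 years of age. It can therefore span from 0 to just under 6 years, against about 2 years prospectively.

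**5. Effect on a reported percentage**

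Section 8.14 reports counts and percentages. At the minimum sizes in section 8.8, one misclassified child moves an incidence by 1/10 = 10 percentage points overall and 1/4 = 25 points in cohort 2.

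**The case against.** A record must be an adverse event before it can be treatment-emergent, and several sections start collection at consent. The retrospective data are described as additional and centre on patterns of use, dose changes and efficacy. A reader might infer that the TEAE tables have no start at consent and will contain retrospective events. The documents do not support that: no section says those events enter the tables. What stands is narrower. The definition does not exclude them, the Safety population limits children rather than dates, and no rule says where retrospective events are reported.

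On the end, collection closes at EOT, and section 4.1.1.2 allows EOT to be done when the drug is stopped. A reader might take 87.5% as a finding. It is one assumed case: a stop at week 13 with EOT still at week 104. For children treated for 2 years, the EOT rule in section 3.2 limits the tail.

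A reader might also infer that off-drug events would be attributed to mexiletine. That does not follow. Causality is judged event by event (section 8.1.4.2), section 8.14 tabulates related TEAEs separately, and the listing carries onset date, action taken and relationship. With about 10 children, off-drug onset can be traced case by case. Nor does a share of follow-up time convert directly into bias in a planned statistic, since no exposure-based rate is specified.

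Finally, a post-dose window is often left to the SAP. Here, though, the protocol itself fixes the TEAE definition, makes it the sole basis of the summaries and states a different window for the primary variable. The SAP would have to depart from one of them.

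**Conclusion.** The mismatch between section 8.1.1 (applied through 8.14) and section 6.1 is real and should be corrected. The missing end is the stronger half: nothing ties event counting to the last dose for a child who stops before 2 years. The start is an ambiguity, limited by the consent-based collection rules, that affects only children already on mexiletine at entry.

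The tables can mix on-treatment events with off-drug or retrospective ones; the protocol does not show that they will. How much off-drug time is included depends on whether a child stops early and on when EOT is then done. For one child followed to week 104, the assumed stops at weeks 13 to 52 give 50% to 87.5% of follow-up, and an EOT at stopping gives close to none. The 10-point and 25-point shifts assume the minimum of 10 children, with 4 in cohort 2, and a child counted as having an event only because of the loose definition.

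**What to change.** 1. In section 8.1.1, define a TEAE as an adverse event with onset or worsening from the later of informed consent and first-ever mexiletine dose, up to the last dose plus a stated fixed interval. The start is then consent for children already treated and first dose for new starters. Anchoring on the first dose after consent would be less suitable, because it drops on-treatment events between consent and the next dose in children already on mexiletine.
2. Use the same window in sections 6.1 and 8.14 and in the synopsis.
3. List retrospective pre-consent events and events after the window separately, outside the TEAE tables. Both stay recorded.
4. Reconcile sections 1.4, 3.2, 3.3.3 and 4.1.1.2 on when EOT occurs after early discontinuation. The choice of timing rests with the sponsor and the clinicians.

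The cost is protocol and SAP wording plus one or two extra listings. TEAE counts may fall slightly, but no data are lost.
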